## 2. PREVIOUS RESEARCH

Postpartum contraception is important because unintended pregnancy rates range from 10%-20% in the first year postpartum.(6, 7) Lactational amenorrhea (LAM) can be effective contraception for up to 6 months.(8) However, many US women stop breastfeeding soon after delivery. By two weeks postpartum, an estimated 59% of US women started supplementation (2) and 37% of women stopped breastfeeding.(9) If sexually active and not using contraception, such women are at risk for unintended pregnancy.

Postpartum visits in the US generally occur 4-6 weeks after delivery.(10) Although 85% of women return for postpartum visits,(11) approximately half of women initiate sexual activity before six weeks postpartum and 82% are sexually active by 12 weeks postpartum.(12) Since ovulation can occur by 4 weeks postpartum in non-breastfeeding women,(13) experts recommend that women who are not exclusively breastfeeding should initiate contraception by 3 weeks postpartum.(14) Some also recommend that the postpartum visit should occur by 2-4 weeks postpartum in order to address contraception, breastfeeding, and postpartum depression,(14, 15) since postpartum depression affects 10%-15% of mothers (16) and can be associated with poor maternal-infant interactions and attachment.(17) Studies of the association of depression and breastfeeding discontinuation are conflicting.(18-20) One study of norethisterone enanthate given within 48 hours of delivery found an increased risk of postpartum depression,(21) but no studies have examined the effect of timing of DMPA administration on postpartum depression, contraceptive use, or breastfeeding.

Breastfeeding has many benefits, including immunologic protection and nutrition for the infant, more rapid uterine involution, decreased postpartum bleeding, and improved infant-bonding.(22) Exclusive breastfeeding for at least six months is recommended by the American College of Obstetricians and Gynecologists and the World Health Organization.(22, 23) However, only 41% of children in the National Immunization Survey were breastfed for 6 months.(24)

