- e. Psychosocial factors that can affect breastfeeding discontinuation, such as family/friend support for breastfeeding, plans for return to work/school, and confidence in ability to breastfeed (18)

**5.5 Subject allocation:** An independent individual will prepare allocation packets using a computer generated random number table. These packets will be placed in a sequentially numbered opaque tamper-resistant sealed envelope. Equal numbers of subjects will be randomly allocated to the following groups:

- 1.) Group 1. DMPA administration prior to hospital discharge.
- 2.) Group 2. DMPA administration at 4-6 weeks after delivery.

**5.6 Admission for delivery:** Research staff will check the hospital census daily for any study subjects. Obstetricians and midwives will be asked to contact the investigators after a subject's delivery and prior to hospital discharge. For women who will enroll in the study postpartum, a member of the postpartum staff or the medical team taking care of the patient will notify the patient of the available study. If the patient is interested in discussing the study with a member of the study team, the postpartum staff member will contact the research office. The verbal permission will be documented by the referring staff member, and filed in the research chart. A member of the research team will proceed with obtaining informed consent, and complete the visit on the postpartum unit. Day of delivery will be considered Day 0. Prior to hospital discharge (and ideally on postpartum day 1), subjects will be interviewed by research staff to assess whether she has initiated breastfeeding and remains eligible for the study. If she has not attempted breastfeeding at least once, does not plan to breastfeed, and/or no longer plans on using DMPA postpartum for contraception, she will be excluded from the study. All other exclusion criteria will again be reviewed to ensure that the subject has not developed any contraindications to DMPA administration

or breastfeeding. If entry criteria are satisfied, the next lowest numbered randomization packet will be opened to determine randomization allocation. All subjects will be informed that pelvic rest is advised for 4-6 weeks.

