#### *OUTCOME ASSESSMENTS*

- A questionnaire about breastfeeding (including psychosocial factors related to breastfeeding and introduction of alternatives to breastmilk) and contraceptive use will be administered at each contact. Timing of lactogenesis II will be assessed at Week 2 unless it occurred prior to discharge. Timing of postpartum sexual activity initiation will also be assessed. At any point when the subject reports cessation of breastfeeding, a questionnaire will be administered to assess reasons for discontinuation.

- The Edinburgh Postnatal Depression Scale (EPDS) will be administered at each contact as a screening tool for postpartum depression.(5) If a subject scores  $\geq 12$  on the EDPS, she will be referred to the Magee Behavioral Health clinic or to a behavioral health clinic of her choice and her primary obstetrician or midwife will be notified.
- Subjects will be asked if they had any visits with their primary obstetrician, midwife, or any other provider since the last contact. Records will be requested from all reported visits.
- The next telephone contact will be scheduled (when applicable).

**5.8 Data analysis:** Analysis will be performed using Stata 10 (StataCorp LP, College Station, TX).

- 1) The primary analyses will use intention-to-treat data. The intention-to-treat group will be defined as all randomized subjects. Infants who are fed pumped breastmilk will be considered as breastfeeding. Exclusive breastfeeding will be defined as breastfeeding without introduction of alternatives to breastmilk. A secondary analysis looking only at women who received at least one injection of DMPA will also be performed.
- 2) Survival analysis will be used for all time series data, including time to discontinuation of breastfeeding and time to introduction of alternatives to breastmilk. Data will be censored at the last date of contact. Breastfeeding will be the outcome variable. The log-rank test will be used for unadjusted comparison of the groups and presented graphically using a Kaplan-Meier curve. Cox proportional hazards model will be used to control for age, race, education, marital status, and prior breastfeeding experience while examining the association between timing of DMPA administration and discontinuation of breastfeeding.

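### Supplementation before randomization is, on a literal reading, an event in the exclusivity log-rank analysis; it dilutes the contrast for Hypothesis 1 and costs power

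*Combined protocol and SAP*

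**What the plan says.** - **Outcome (section 5.8, item 1).** "Exclusive breastfeeding will be defined as breastfeeding without introduction of alternatives to breastmilk". No lower time limit is attached. The analysis set is everyone randomized.
- **Method (section 5.8, item 2).** Survival analysis covers several outcomes, "including time to discontinuation of breastfeeding and time to introduction of alternatives to breastmilk". The log-rank test and Kaplan-Meier curve serve these comparisons. The Cox model is described only for stopping breastfeeding. No time origin is given.
- **Clock (section 5.6).** "Day of delivery will be considered Day 0".
- **Randomization (section 5.6).** "Prior to hospital discharge (and ideally on postpartum day 1), subjects will be interviewed by research staff"; then, "If entry criteria are satisfied, the next lowest numbered randomization packet will be opened to determine randomization allocation".
- **Feeding test at that point (section 5.6).** A woman is excluded on feeding grounds on this condition: "If she has not attempted breastfeeding at least once, does not plan to breastfeed". Formula already given is not a reason for exclusion.
- **Background (section 2).** "By two weeks postpartum, an estimated 59% of US women started supplementation".

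Nothing in the plan excludes, resets, stratifies or adjusts for supplementation before randomization. Introduction of alternatives is listed as a questionnaire topic for the telephone contacts, the first of which is at week 2. It is not listed among the items collected in hospital.

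**The concern.** Some infant feeding takes place between delivery and the opening of the packet. If an infant receives formula in that interval, the mother has met the event definition before she belongs to either group. Such events occur at the same expected rate in both arms and carry no information on the timing of the injection.

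This matters because exclusive breastfeeding for 6 months is Hypothesis 1. Early formula supplementation is also the route by which section 2 suggests an early progestin might do harm. An analysis of that route should separate supplementation after allocation from supplementation before it. If the plan leaves this open, the analyst will have to choose the time origin and the at-risk set later, possibly with data in hand.

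**Working it through.** **1. The plan's own figure (section 5.9).** Inputs: 0.35 vs 0.60, two-sided Fisher's exact test, significance level 0.05, 80% power. Exact enumeration gives power 0.8095 at 70 per group and 0.7992 at 69, so 70 is reproduced. For enrolment, 140/0.85 = 164.7, rounded up to 165 randomized; 165/0.90 = 183.3, rounded up to 184. Randomized women per arm: 165/2 = 82.5, taken as 83. These rates are for any breastfeeding at 6 months, not for exclusivity.

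**2. Order of events.** Delivery (Day 0), then feeding in hospital, then interview (ideally day 1, otherwise before discharge), then packet opened. The event definition has no start, so it reaches back to delivery.

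**3. Dilution of the 6-month contrast.** Let q be the share of each arm supplemented before randomization, and let 0.60 and 0.35 apply to the remaining women. The proportion still exclusive at 6 months among all randomized women is (1 − q) × 0.60 vs (1 − q) × 0.35, so the difference is 0.25 × (1 − q). The documents do not give q. The 59% by two weeks includes supplementation at times after randomization, so it is at most an upper reference. Shares of 10, 20 and 30% are assumed.

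| q | Proportions, all randomized | Difference | Fisher power, 70 per group | Fisher power, still exclusive only (n per group) |
|---|---|---|---|---|
| 0 | 0.60 vs 0.35 | 0.250 | 0.81 | 0.81 (70) |
| 0.1 | 0.54 vs 0.315 | 0.225 | 0.72 | 0.78 (63) |
| 0.2 | 0.48 vs 0.28 | 0.200 | 0.62 | 0.69 (56) |
| 0.3 | 0.42 vs 0.245 | 0.175 | 0.53 | 0.65 (49) |

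**4. Log-rank test, which is the planned method.** Simulation with 83 per arm, exponential times matching the 6-month proportions, 15% lost at uniform times, and a share q in each arm given an event on day 1.

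| q | 0.60 vs 0.35: counted | removed | 0.30 vs 0.15: counted | removed |
|---|---|---|---|---|
| 0.1 | 0.80 | 0.87 | 0.60 | 0.66 |
| 0.2 | 0.67 | 0.82 | 0.50 | 0.61 |
| 0.3 | 0.55 | 0.76 | 0.43 | 0.55 |

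At q = 0 the first pair gives about 0.90. Figures are good to about 0.02. The second pair shows the effect if true exclusivity is lower, and is also an assumption. Removing the early events gives higher power in every row, despite fewer women.

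**5. Type I error.** If timing has no effect, the early events are balanced in expectation and so are the later ones. The test keeps its level.

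**6. What is not touched.** The Cox model concerns stopping breastfeeding, for which formula is not an event. The sample size in section 5.9 concerns any breastfeeding.

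**The case against.** **The plan does not say that it counts these events.** This stands. Section 5.8 names no time origin, and the Day 0 statement fits the telephone windows in section 5.7 as well as it fits the survival analysis. Counting follows from the literal definition, not from an explicit instruction. The gap still needs closing, because no other handling is specified.

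**The all-randomized contrast is a valid effect.** This also stands. An infant given formula on the first day has not been exclusively breastfed for 6 months, and the difference among all randomized women is a proper intention-to-treat quantity. A reader might infer that the planned analysis is biased. It is not: it answers a more diluted question with less power.

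**The estimated hazard ratio would be pulled toward 1.** A reader might infer that the trial will report such a ratio. Under the assumptions above, a one-step estimate from the log-rank statistic falls from ln 0.35 / ln 0.60 = 2.06 to about 1.82/1.66/1.56. The plan, however, specifies no Cox model for introduction of alternatives, so it does not commit to that estimate.

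**The size is assumed.** Correct. Neither q nor any exclusivity rate for this population is in the documents. If 0.60 and 0.35 were instead the proportions among all randomized women, the early events would already be inside them. Fisher power at 70 per group would then stay at about 0.81 whatever the share, and the log-rank loss would be smaller. Restriction would still gain power.

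**Balance between arms makes the issue harmless.** This does not stand. Balance protects the level of the test but not its power.

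**Conclusion.** The concern holds in a limited form. The exclusivity analysis has no stated time origin, and its literal definition admits events that precede allocation and cannot depend on it. The consequence is a diluted contrast and lower power for Hypothesis 1, with type I error intact.

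For an assumed share of 10/20/30%, counting the events costs about 7/15/21 points of log-rank power compared with removing them (0.87 − 0.80, 0.82 − 0.67, 0.76 − 0.55). At the lower rates of 0.30 vs 0.15 the cost is 6/11/12 points. Both sets of figures are illustrations. They rest on the assumed share, on rates borrowed from any breastfeeding and applied to women not yet supplemented, and on exponential times. If few infants are supplemented before the packet is opened, the loss is small.

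The documents do not support reading this as a fault in the Cox model, in the stated sample size, or in the validity of the intention-to-treat comparison.

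**What to change.** 1. **Section 5.6.** At the existing interview, before the packet is opened, record whether the infant has been given anything other than breastmilk.
2. **Section 5.8.** State that time to introduction of alternatives runs from randomization, among women still exclusive at that moment. Equivalently, use a log-rank test from randomization in all randomized women, stratified by the recorded status. The already-supplemented stratum can have no first introduction after randomization, so it contributes nothing to the test. Because status is fixed before allocation, either form keeps the randomized comparison valid.
3. **Keep alongside.** Report the all-randomized analysis from birth as well. Leave time to stopping any breastfeeding unchanged.
4. **Women already randomized.** Assign status only from records made before allocation, such as the inpatient feeding record. Do not use recall at the 2-week call: it follows an allocation that the woman knows, so membership of the subset could depend on it. Where no such record exists, keep the woman in the all-randomized analysis only.

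The cost is one question at an interview already held and a sentence or two in section 5.8. The downside is that the exclusivity analysis rests on a baseline-defined subset, and status may be missing for women enrolled earlier.

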## ABSTRACT

In the United States, depot medroxyprogesterone acetate (DMPA) is frequently administered prior to hospital discharge with the belief that women who delay initiation of DMPA may face higher risk of unintended pregnancy and that administration postpartum has little to no negative effect on breastfeeding. Administering DMPA to breastfeeding women has not been widely questioned because the limited existing studies do not show any adverse impact of DMPA on breastfeeding. However, these studies used inappropriate control groups and did not control for prior lactation experience.(1-3) We recently conducted a randomized controlled trial (RCT) which found that significantly fewer women who underwent immediate postplacental levonorgestrel-releasing IUD (LNG-IUD) placement continued to breastfeed at 6 months compared to those who underwent insertion at 6-8 weeks postpartum.(4) Since systemic levels of progestins are much less with the LNG-IUD compared to DMPA, we became concerned about potential effects of administering DMPA immediately postpartum.

We therefore propose to enroll 184 women who plan to breastfeed and use DMPA postpartum in a RCT to investigate whether the timing of postpartum administration of DMPA (prior to hospital discharge vs. 4-6 weeks postpartum) affects the duration or exclusivity of breastfeeding among women who plan to breastfeed their infants. Secondary outcomes will include rates of use of highly effective contraception (defined as DMPA, IUD, implant, sterilization, or lactational amenorrhea) and postpartum depression. Outcomes will be assessed by phone at 2, 4, 6, 8, 12, 16, 20, 24, and 28 weeks postpartum.

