## 1. SPECIFIC AIMS AND HYPOTHESES

### SPECIFIC AIMS:

To compare the effect of administering postpartum intramuscular (IM) depot medroxyprogesterone acetate (DMPA) prior to hospital discharge compared to 4-6 weeks after delivery on: 1) exclusivity and duration of breastfeeding; 2) use of highly effective contraception; and 3) postpartum depression

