- 3) Normally distributed continuous variables will be compared using Student's t-tests. The Mann-Whitney rank-sum test will be used to compare other continuous variables. Proportions will be compared using chi-square tests or Fisher's exact tests as appropriate.

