### **5.9 Number of subjects and statistical power**

We previously found in a randomized study comparing postplacental and delayed LNG-IUD insertions that only 9% of subjects receiving a postplacental LNG-IUD were breastfeeding at 6 months compared to 41% of subjects receiving a delayed LNG-IUD.(4) We expect breastfeeding continuation rates will be higher in this study since we will be recruiting women who intend to breastfeed. A sample size of 70 per group achieves 80% power ( $\beta=0.20$ ) to detect a difference of 25% between the null hypothesis that the proportion of breastfeeding continuation at 6 months is 0.60 for both groups and the alternative hypothesis that the proportion in group 1 is 0.35 with a significance level of 0.05. With an estimated 10% discontinuation rate prior to randomization and 15% loss-to-follow-up, we plan to enroll 184 subjects

total. Sample size calculations were performed with the two-sided Fisher's Exact test using PASS 2005 (NCSS, Kaysville, UT).

Group 1 (on discharge)	Group 2 (4-6 weeks)	Sample size per group	Total sample size	Including 10% discontinuation/15% LTFU
0.15	0.4	56	112	147
0.25	0.5	64	128	168
0.35	0.6	70	140	184
0.45	0.7	69	138	182

**5.10 Project management:** The study will be coordinated by the Center for Family Planning Research, located in Magee-Womens Hospital at the University of Pittsburgh, which has performed a broad array of family planning research since 1994. The principal investigator and the research coordinator will be responsible for daily monitoring of subject safety. Enrollment, outcomes, and adverse events will be reviewed during biweekly meetings of the investigators and staff. The office has locked storage areas for maintaining subject files. All computers used for database management have firewalls and antivirus software that are updated regularly.

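### Two breastfeeding outcomes stand unranked at primary level with no deciding test or alpha rule; if a significant result on either counts, the false-positive rate is about 7–10% with one test each

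*Combined protocol and SAP*

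**What the plan says.** The Abstract asks whether the timing of DMPA "affects the duration or exclusivity of breastfeeding among women who plan to breastfeed their infants". Aim 1 likewise pairs "exclusivity and duration of breastfeeding" in one item. The Abstract's list of secondary outcomes ("Secondary outcomes will include rates of use of highly effective contraception", then postpartum depression) contains no breastfeeding outcome, so both stay at primary level and neither is ranked.

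On analysis, section 5.8 item 2 covers both outcomes: "Survival analysis will be used for all time series data, including time to discontinuation of breastfeeding and time to introduction of alternatives to breastmilk". For the unadjusted analysis it says: "The log-rank test will be used for unadjusted comparison of the groups and presented graphically using a Kaplan-Meier curve". That sentence makes no distinction between the two outcomes. The adjusted analysis is narrower, since discontinuation is the only outcome named for it: "Cox proportional hazards model will be used to control for age, race, education, marital status, and prior breastfeeding experience".

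Item 3 adds "Proportions will be compared using chi-square tests or Fisher's exact tests as appropriate", without naming an outcome or a time point.

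Hypothesis 1 is about exclusive breastfeeding for 6 months. Section 5.9 is about continuation of any breastfeeding at 6 months: 0.60 in both groups under the null, against "the alternative hypothesis that the proportion in group 1 is 0.35 with a significance level of 0.05", using a two-sided Fisher test. Section 5.8 itself states no significance level.

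**The concern.** The two places where a reader would look for the primary outcome, Hypothesis 1 and the sample-size section, point to different outcomes. The analysis section then treats both alike. It also opens with a log-rank test, although the trial was sized on a comparison of proportions. Nothing says what the trial concludes if one outcome is significant and the other is not, or if the methods disagree on the same outcome.

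The research question is worded so that an effect on either outcome would answer it. Read that way, the trial has at least two chances to report an effect, and the 0.05 used for sizing no longer describes the risk of a false report. Section 3 says the results should help clinicians advise patients about early DMPA, so a chance finding would have consequences. Leaving the choice open also allows the deciding outcome or test to be picked after the data are seen.

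**Working it through.** **1. The plan's own figure.** Inputs from section 5.9: 0.35 vs 0.60, two-sided Fisher, alpha 0.05, 80% power, 70 per group, 10% lost before randomization, 15% lost to follow-up.

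- Exact Fisher power by enumeration is 0.7992 with 69 per group and 0.8095 with 70, so 70 is reproduced.
- Enrolment: 140 / (0.90 × 0.85) = 140 / 0.765 = 183.01, rounded up to 184. Reproduced.

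The 0.05 therefore belongs to one two-sided Fisher test of one outcome, any breastfeeding at 6 months. The actual size of that test with 70 per group and a common rate of 0.60 is 3.2%.

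**2. What is assigned to each outcome.**

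| | Discontinuation (duration) | Alternatives introduced (exclusivity) |
|---|---|---|
| Log-rank, 5.8 item 2 | yes | yes |
| Adjusted Cox, 5.8 item 2 | yes | not named |
| 6-month proportion, 5.8 item 3 | implied by 5.9 | inferred only, from Hypothesis 1 |
| Sample size, 5.9 | yes | no |
| Hypothesis 1 | no | yes |

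**3. One test per outcome.** For two tests of size 0.05 whose statistics have correlation ρ under the null:

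P(at least one significant) = 1 − P(|Z₁| < 1.96 and |Z₂| < 1.96), with (Z₁, Z₂) bivariate normal.

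| ρ | 0 | 0.3 | 0.5 | 0.7 | 0.8 | 0.9 |
|---|---|---|---|---|---|---|
| Rate | 9.75% | 9.5% | 9.1% | 8.4% | 7.8% | 7.0% |

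At ρ = 0 this is 1 − 0.95² = 0.0975. The documents give no ρ, hence the range.

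**4. Several methods per outcome.** Null trials were simulated in ten scenarios of 1,500 to 3,000 trials each. Taken from the plan: 1:1 allocation, 166 randomized (184 × 0.90 = 165.6) and 15% loss. Assumed, because the documents are silent:

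- a 6-month any-breastfeeding rate common to both arms of 0.60 (0.35 in one scenario);
- a 6-month exclusive rate of 10–40%;
- a latent correlation between the two times of 0 to 0.8;
- covariate log hazard ratios of 0 to 0.4 per SD.

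| Any one of these below 0.05 counts | Range over scenarios |
|---|---|
| Log-rank on each outcome | 7.3–9.8% |
| Log-rank and 6-month proportion test on each | 9.6–13.5% |
| The same four, plus Cox for discontinuation | 11.0–15.8% |

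The Monte Carlo standard error is about 0.6 to 1.0 points. The first row agrees with step 3: the two log-rank statistics had correlations of 0.44 to 0.73.

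**5. After a change.** One deciding comparison at two-sided 0.05 holds the rate at 5% or less. If alpha is split instead, at 0.025 per outcome and with the same 0.35 vs 0.60 contrast, the formula is

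n₀ = [z_α/2 √(2p̄q̄) + z_β √(p₁q₁ + p₂q₂)]² / d², then n = (n₀/4)[1 + √(1 + 4/(n₀d))]²

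with p̄ = 0.475 and d = 0.25.

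- At 0.05: n₀ = (1.960 × 0.7062 + 0.8416 × 0.6837)² / 0.0625 = 61.4, so n = 69.2, rounded up to 70, which matches 5.9.
- At 0.025: n₀ = (2.241 × 0.7062 + 0.8416 × 0.6837)² / 0.0625 = 74.5, so n = 82.3, rounded up to 83. Enrolment is 166 / 0.765 = 216.99, or 217.

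**The case against.** The best defence is that the plan sets out ordinary reporting. The log-rank test is the unadjusted comparison and the Cox model the adjusted one. They estimate the same effect and are not separate chances to win. Section 5.9 shows which outcome the trial was built around, and no sentence says that any single significant result proves an effect. Much of this stands: the any-win rule is a reading of the research question, not a rule the plan states. But no passage gives the log-rank or Cox result a supportive role, and Hypothesis 1 contradicts the view that 5.9 settles the primary outcome. Two unranked outcomes are enough for the point, even if each has only one test.

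A reader might go further and infer that each outcome is tested with log-rank, Cox and a 6-month proportion test, all at 0.05, so that the error rate is about 14–16%. The documents do not support this. The Cox model is tied to discontinuation only, the proportions sentence is generic, and 0.05 appears only in the sample-size section. The six-test simulation gave 11–19% depending on assumptions, so a narrow figure is not a property of the plan.

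Nor does the plural in the primary-analyses sentence of 5.8 item 1 show several co-primary tests. It defines the intention-to-treat population, in contrast with the analysis of women who received at least one injection.

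**Conclusion.** The point holds in a limited form. The plan has two breastfeeding outcomes at primary level and names no deciding outcome, deciding test, testing order or alpha control. Its first hypothesis and its sample size concern different outcomes.

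If significance on either outcome is read as an effect on breastfeeding, the false-positive rate is about 7–10%. That assumes one test per outcome of true size 5%, with correlation from 0.9 down to 0. It suits the log-rank pair; Fisher's test is conservative, so a pair of Fisher tests would inflate less. The figure of roughly 10–16% applies only if several methods per outcome can each carry the claim, and it rests on assumed hazards, exclusive-breastfeeding rates, covariate strengths and correlations.

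A reader might also take disagreement between methods as evidence of inflated error. Under a true 0.35 vs 0.60 difference, log-rank, Cox and Fisher on any breastfeeding disagreed in 18.5% of 1,500 simulated trials. Some disagreement is expected with a real effect and moderate power. It shows only why the deciding test should be named beforehand.

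The correction is inexpensive and worth making; the point does not invalidate the design.

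**What to change.** Add a testing rule to section 5.8 before any outcome is compared by arm.

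1. Reconcile Hypothesis 1 with section 5.9 first, because the order of testing depends on it.
2. Name one primary breastfeeding outcome and one deciding test at two-sided 0.05. If it is any breastfeeding at 6 months by Fisher's test, 5.9 applies unchanged. If exclusivity goes first, state that the documents give no planning rates for it, so the 80% power is not supported for that outcome.
3. Test the other breastfeeding outcome confirmatorily, with its own single named test, only if the first is significant. Holm across the two is an alternative, but its first step is at 0.025. Keeping 80% power at that step takes about 83 per group, or 217 enrolled, under the same contrast.
4. Report the remaining methods for each outcome as supportive, with estimates and 95% confidence intervals.

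Contraception and depression need no relabelling, since the Abstract already makes them secondary.

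The cost is one paragraph. With the fixed sequence and the sized outcome first, no extra data or patients are needed. The downside is that the second outcome, which may be the one in Hypothesis 1, cannot be claimed as confirmed if the first test is not significant. A favourable result from a supportive method alone would no longer count as proof.
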